### 1.2.2.1 Axitinib and Pembrolizumab

A notable result that was recently reported was the combination of axitinib with pembrolizumab versus sunitinib in an open-label phase III trial for patients with treatment-naïve advanced RCC [18]. The estimated percentage of patients alive at 12 months was significantly higher with axitinib + pembrolizumab (89.9% versus 78.3%, HR 0.53), as was median PFS (15.1 versus 11.1 months, HR 0.69), with an objective response rate of 59% with axitinib + pembrolizumab. Grade 3 or higher adverse events of any cause were seen in 76% of patients receiving axitinib + pembrolizumab, with 63% of patients experiencing a Grade 3 or higher adverse event attributed to the combination therapy. Most frequent treatment-related adverse events ( $\geq$ Grade 3) were hypertension (21%), elevations in alanine aminotransferase (12%), diarrhea (7%), and elevations in aspartate aminotransferase (7%). Adverse events regardless of attribution led to discontinuation of either drug (31%), discontinuation of both drugs (11%), interruption of either drug (70%), and dose reduction of axitinib (20%).

## 1.3 Rationale for the Proposed Study

### 1.3.1 Rationale for a Perioperative Study in Subjects Eligible for CN/MET

Historical studies have demonstrated the clinical efficacy of CN in association with immunotherapy. In SWOG-8949, advanced RCC subjects treated with CN in addition to interferon-alpha (IFN- $\alpha$ ) had a significant improvement in OS (11 vs 8 months) compared to those treated with IFN- $\alpha$  alone [23]. Similar results were seen in a European Organisation for Research and Treatment of Cancer (EORTC) study (same treatment as SWOG study), with a significant improvement in OS in favor of CN in addition to immunotherapy [24]. The clinical benefit of CN appears to persist in the TKI era as well; results from the International Metastatic Renal Cell Carcinoma Database Consortium showed a median OS of 20.6 months for subjects who underwent CN vs 9.5 months for those who received only systemic therapy [25].

Furthermore, small studies of MET in select patient populations with limited tumor burden, either upfront or as consolidation (in addition to either systemic TKI or immunotherapy), may provide additional clinical benefit [26, 27]. No prospective studies exist, but multiple retrospective analyses, both in the pre-TKI and TKI era, have demonstrated the significant clinical benefit of MET, particularly in cases where a complete (R0) resection could be achieved [28-32].

Finally, the efficacy and safety of perioperative treatment for subjects with metastatic and advanced RCC prior to CN has been shown in multiple prospective studies. Perioperative TKI treatment has demonstrated tumor shrinkage in the range of 13-22%, with a significant proportion of subjects who were previously deemed unresectable able to proceed with surgical resection [27, 33-36]. Just as importantly, there does not appear to be increased risk of overall surgical morbidity or mortality associated with perioperative therapy. One specific concern is the risk of delayed wound healing in subjects receiving TKI therapy; the results of existing studies are conflicting, as some studies have shown delayed wound healing in up to 20-25% of subjects, while other studies have shown no evidence of delayed wound healing.

#### 1.3.1.1 Rationale for Fixed Dose Pembrolizumab

The planned dose of pembrolizumab for this study is 200 mg Q3W followed by 400 mg Q6W.

Based on the totality of data generated in the Keytruda development program, 200 mg Q3W is the appropriate dose of pembrolizumab for adults across all indications and regardless of tumor type.

A 400 mg Q6W dosing regimen of pembrolizumab is expected to have a similar benefit-risk profile as 200 mg Q3W, in all treatment settings in which 200 mg Q3W pembrolizumab is currently appropriate [37]. Specifically, the dosing regimen of 400 mg Q6W for pembrolizumab is considered adequate based on modeling and simulation (M&S) analyses, given the following rationale:

- Pharmacokinetic (PK) simulations demonstrating that in terms of pembrolizumab exposures:
  - Average concentration over the dosing interval ( $C_{avg}$ ) (or area under the curve [AUC]) at 400 mg Q6W is similar to the approved 200 mg Q3W dose, thus bridging efficacy between dosing regimens.
  - Trough concentrations ( $C_{min}$ ) at 400 mg Q6W are generally within the range of those achieved with 2 mg/kg or 200 mg Q3W in the majority (>99%) of patients.
  - Peak concentrations ( $C_{max}$ ) at 400mg Q6W are well below the  $C_{max}$  for the highest clinically tested dose of 10 mg/kg Q2W, supporting that the safety profile for 400 mg Q6W should be comparable to the established safety profile of pembrolizumab.
  - Exposure-response (E-R) for pembrolizumab has been demonstrated to be flat across indications, and OS predictions in melanoma and non-small cell lung cancer (NSCLC) demonstrate that efficacy at 400 mg Q6W is expected to be similar to 200 mg or 2mg/kg Q3W, given the similar exposures; thus, 400 mg Q6W is expected to be efficacious across indications.

### 1.3.2 Overarching Objective

Here we propose perioperative therapeutic combinations, with pembrolizumab (KEYTRUDA, Merck) as the treatment backbone, in patients with locally advanced or metastatic RCC who are eligible for CN or MET. The study will include multiple treatment cohorts into which subjects will be accrued, and after 9 weeks of preoperative therapy, subjects will undergo CN or MET. Paired tumor specimens (pre- and on-treatment) will be collected for molecular analysis and allow for unprecedented translational investigation of combination immune therapeutic approaches in human mRCC specimens. Subjects who experience clinical benefit (CR, PR, or SD) during the preoperative treatment period will be offered continued pembrolizumab-based therapy (400 mg Q6W) following CN or MET.

## 1.4 Correlative Studies

### 1.4.1 Correlative Studies Background

Correlative science to understand the biologic and immunologic impact of pembrolizumab-based therapy in advanced RCC, and to identify candidate biomarkers of response, resistance, or toxicity, is an integral part of this study. Sample collection for the correlative studies are outlined in the Procedure Manual. Correlative studies may include but are not limited to:

- Clinical correlatives:
  - Pathologic response rate and R0 resection rates
  - Clinical efficacy of continued pembrolizumab-based therapy
- Scientific correlatives:
  - Changes in tumor-infiltrating immune cells (TIICs)
  - Changes in frequency and numbers of circulating T cells
  - Comprehensive assessment of the tumor microenvironment
  - Transcriptional profiling of tumor microenvironment constituents
  - Changes in T cell repertoire
  - Molecular profiling to explore biomarkers of response
  - Change in neoepitope burden
- Correlative research will be performed on:
  1. Baseline primary and/or metastatic biopsies.
  2. CN and/or MET specimens.
    - If CN or MET is not feasible, post-treatment tumor core biopsies should be performed when safe and feasible to allow acquisition of adequate specimens for correlative studies
  3. Serial blood samples.
  4. Archival tumor samples originally obtained prior to study consent (when available).

### 1.4.2 Biomarker Research

Cancer immunotherapies represent an important and novel class of antitumor agents. However, the mechanism of action of these exciting new therapies is not completely understood and much

remains to be learned regarding how best to leverage these new drugs in treating patients. Thus, to aid future patients, it is important to investigate the determinants of response or resistance to cancer immunotherapy and other treatments administered, as well as determinants of AEs in the course of our clinical studies. These efforts may identify novel predictive/PD biomarkers and generate information that may better guide single-agent and combination therapy with immuno-oncology drugs. To identify novel biomarkers, biospecimens (ie, blood components, tumor material) will be collected to support analyses of cellular components (eg, protein, DNA, RNA, metabolites) and other circulating molecules. Investigations may include but are not limited to:

### Tumor PD-L1 Expression

To date, tumor PD-L1 expression had not proven itself as a reliable predictive biomarker of response in mRCC. In the phase III CheckMate 025 study, responses to nivolumab were identical in the PD-L1 negative and positive groups. More recently, the preliminary analysis of the ongoing phase II study of atezolizumab and bevacizumab in treatment-naïve mRCC (NCT01984242) was reported. In the atezolizumab monotherapy arm, again, there was no significant difference in response rate between the PD-L1 negative and positive groups. However, in the atezolizumab/bevacizumab combination arm, the response rate of PD-L1 positive subjects was much higher[38]. Thus in this study, we propose an investigation of tumor PD-L1 expression as a potential biomarker in subjects who receive combination checkpoint inhibitor/VEGF-inhibitor therapy.

### Immune-related Gene Expression Profile (GEP)

Intratumoral expression levels of select genes will be analyzed using an analytically validated platform. Association between the immune-related GEP and response to pembrolizumab has been established using these genes in melanoma and in cancers from clinical studies KN012 (head and neck, bladder, and gastric cancers) and KN028 (ovarian, esophageal, and other cancers). Data from these cohorts has been used to derive a GEP, which combines the expression levels of several key genes into a single scalar score [40]. The pattern of association in the esophageal cohort of KN028 using a prototype GEP suggested the ability to identify patients who may not respond to pembrolizumab by identifying tumors that have low values of the GEP. The GEP includes genes from immune-regulatory pathways and a GEP score will be tested for association with response to pembrolizumab in retrospective fashion. The relationship between GEP and the probability of response will be used to develop cut-offs that may have high clinical utility.

### Tumor and Blood RNA Analyses

Both genome-wide and targeted mRNA expression profiling and sequencing in tumor tissue and in blood may be performed to define gene signatures that correlate to clinical response to treatment with pembrolizumab or other immunotherapies. Pembrolizumab induces a response in tumors that likely reflects an inflamed/immune phenotype. Specific immune-related gene sets (ie, those capturing interferon-gamma transcriptional pathways) may be evaluated and new signatures may be identified. Individual genes related to the immune system may also be evaluated (eg, IL-10). MicroRNA profiling may also be pursued as well as exosomal profiling.

### Proteomics and IHC using blood or tumor

Tumor and blood samples from this study may undergo proteomic analyses (eg, PD-L1 IHC). PD-L1 protein level in tumor sections, assessed by IHC, has been shown to correlate with response to pembrolizumab in patients with NSCLC, and an IVD device has been developed for use with pembrolizumab in NSCLC. Preliminary data indicates that this association may also be true in additional cancer types (ie, triple negative breast cancer, head and neck, and gastric). Additional tumor or blood-derived proteins may also correlate with response to pembrolizumab. Therefore, tumor tissue may be subjected to proteomic analyses using a variety of platforms that could include but are not limited to immunoassays and liquid chromatography/mass spectrometry. This approach could identify novel protein biomarkers that could aid in patient selection for pembrolizumab therapy.

### Genetic (DNA) analyses from tumor

The application of new technologies, such as next generation sequencing, has provided scientists the opportunity to identify tumor-specific DNA changes (ie, mutations, methylation status, microsatellite instability). Key molecular changes of interest to immuno-oncology drug development include the mutational burden of tumors and the clonality of T-cells in the tumor microenvironment. Increased mutational burden (sometimes referred to as a 'hyper-mutated' state) may generate neo-antigen presentation in the tumor microenvironment. To conduct this type of research, it is important to identify tumor-specific mutations that occur across all genes in the tumor genome. Thus, genome-wide approaches may be used for this effort. Note that in order to understand tumor-specific mutations, it is necessary to compare the tumor genome with the germline genome. Microsatellite instability may also be evaluated as this is an important biomarker for some cancers (ie, colorectal cancer). Circulating tumor DNA and/or RNA may also be evaluated from blood samples.

### Germline (blood) genetic analyses (e.g., single-nucleotide polymorphism [SNP] analyses, whole exome sequencing, whole genome sequencing)

This research may evaluate whether genetic variation within a clinical study population correlates with response to the treatment(s) under evaluation. If genetic variation is found to predict efficacy or AEs, the data might inform optimal use of therapies in the patient population. Furthermore, it is important to evaluate germline DNA variation across the genome in order to interpret tumor-specific DNA mutations. Finally, MSI may be evaluated as this is an important biomarker for some cancers (ie, colorectal cancer).

### Planned Genetic Analysis

Genetic variation may impact a patient's response to therapy, susceptibility to, and severity and progression of disease. Variable response to therapy may be due to genetic determinants that impact drug absorption, distribution, metabolism, and excretion; mechanism of action of the drug; disease etiology; and/or molecular subtype of the disease being treated. Therefore, where local regulations and Institutional Review Board (IRB)/Ethics Review Committee (ERC) allow, a sample will be collected for DNA analysis from consenting subjects.

DNA samples will be used for research related to the study treatment(s), the disease under study and related diseases. They may also be used to develop tests/assays including diagnostic tests

related to the disease under study, related diseases, and study drug(s). Genetic research may consist of the analysis of one or more candidate genes or the analysis of genetic markers throughout the genome or analysis of the entire genome (as appropriate).

DNA samples will be analyzed for variation across the entire genome. Analyses may be conducted if it is hypothesized that this may help further understand the clinical data.

The samples may be analyzed as part of a multi-study assessment of genetic factors involved in the response to understand study disease or related conditions.

#### Microbiome Analysis of Stool

Stool samples will be collected and a stool questionnaire will be completed to assess the microbiome associated with clinical activity. This research may help identify factors predictive of pembrolizumab response and resistance and novel targets for cancer immunotherapy.

### **1.4.3 Future Biomedical Research Specimen Collection**

The investigator will conduct Future Biomedical Research on specimens consented for future biomedical research during this clinical trial.

Such research is for biomarker testing to address emergent questions not described elsewhere in the protocol (as part of the main study) and will only be conducted on specimens from appropriately consented participants. The objective of collecting/retaining specimens for FBR is to explore and identify biomarkers that inform the scientific understanding of diseases and/or their therapeutic treatments. The overarching goal is to use such information to develop safer, more effective drugs/vaccines, and/or to ensure that participants receive the correct dose of the correct drug/vaccine at the correct time. Decisions on Future Biomedical Research will be made by the Joint Steering Committee.

#### **1.4.3.1 Future Biomedical Research Samples**

The following specimens could be obtained as part of Future Biomedical Research:

- Leftover tumor for future research
- Leftover DNA and RNA from Correlative Studies
- Leftover plasma and serum from Biomarker Studies
- Leftover peripheral blood mononuclear cells (PBMC) from whole blood from correlative studies
- Microbiome

## 2 Objectives and Endpoints of the Study

### 2.1 Objectives

#### 2.1.1 Primary

- To determine the impact of pembrolizumab-based therapy on the composition, phenotype, and function of tumor-infiltrating immune cells (TIIICs) in subjects with advanced RCC undergoing CN/MET

#### 2.1.2 Secondary

- To determine the clinical efficacy of preoperative pembrolizumab-based therapy in subjects with advanced RCC undergoing CN/MET
- To explore the clinical efficacy of continued pembrolizumab-based therapy following CN/MET in subjects with advanced RCC
  - Subjects who achieve R0 resection (NED, negative margins) or R1 resection (microscopic disease, positive margins) after preoperative treatment will receive continued pembrolizumab-based combination therapy for up to 1 year (9 cycles) following CN/MET, or until disease progression, death, unacceptable toxicity, or withdrawal from study, whichever occurs first.
  - Subjects who achieve R2 resection (macroscopic disease after surgery) after preoperative treatment, or who do not undergo nephrectomy after achieving pre-operative radiographic CR, will receive continued pembrolizumab-based combination therapy for up to 2 years (18 cycles) following CN/MET, or until disease progression, death, unacceptable toxicity, or withdrawal from study, whichever occurs first.
- To determine the safety and tolerability of pembrolizumab-based therapy in subjects with advanced RCC undergoing CN/MET

#### 2.1.3 Exploratory

##### 2.1.3.1 Clinical

- To explore the clinical efficacy of preoperative pembrolizumab-based therapy in subjects with advanced RCC, by pathologic response

##### 2.1.3.2 Scientific

- To explore the relationship between changes in TIIICs and clinical efficacy in subjects with advanced RCC treated with pembrolizumab-based therapy
- To characterize changes in the frequency and number of circulating T cells induced by pembrolizumab-based therapy in subjects with advanced RCC

- To determine the impact of pembrolizumab-based therapy on the composition and phenotype of the tumor microenvironment (including tumor and stromal cells) in subjects with advanced RCC
- To determine whether locally advanced versus metastatic RCC exhibit differences in immune composition or phenotype at baseline and in response to pembrolizumab-based therapy
- To determine the change in T cell repertoire within the tumor and blood induced by pembrolizumab-based therapy in subjects with advanced RCC
- To explore molecular profiles to identify potentially predictive biomarkers for subjects with advanced RCC treated with immunotherapy

## 2.2 Endpoints

### 2.2.1 Primary

- The proportion of subjects with  $\geq 2$ -fold increase in the number of TICs between pre- and post-treatment tumor specimens.

### 2.2.2 Secondary

- The clinical efficacy of preoperative pembrolizumab-based therapy in subjects with advanced RCC will be assessed by ORR, defined as CR or PR per Response Evaluation Criteria in Solid Tumors (RECIST) 1.1, modified to allow a maximum of 10 target lesions or 5 target lesions per organ.
- The clinical efficacy of continued pembrolizumab-based therapy in subjects with advanced RCC will be assessed as follows:
  - In subjects who obtain CR or PR/SD with R0 resection and are treated 1 year of pembrolizumab-based therapy:
    - 1-year and 2-year disease-free survival (DFS) rate, and median DFS
  - In subjects who obtain PR/SD and have residual disease following CN/MET and are treated with 1 year of pembrolizumab-based therapy:
    - 1-year and 2-year PFS rate, and median PFS
- Safety will be assessed and reported using National Cancer Institute (NCI) Common Terminology Criteria for Adverse Events (CTCAE) version 5.0
  - Surgical complications will be assessed according to the Clavien-Dindo classification (Appendix 3)

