- Subjects with PD during the preoperative treatment period who, in the opinion of the treating physician and principal investigator, are likely to benefit from CN/MET AND in whom surgery is safe and feasible, may proceed with CN/MET on study. Subjects in whom CN/MET is unlikely to provide benefit OR surgery is not safe and feasible, may proceed with tumor biopsy on study, if safe and feasible. Subjects will withdraw from study participation following CN/MET or tumor biopsy. If CN/MET and tumor biopsy are not safe and feasible and not in the best interests of the subject, the subject will withdraw from study participation immediately. The risk of disease progression during the preoperative treatment period is 10% [18]. The use of anti-PD-1 antibodies has now become standard of care. As a result, participants are receiving treatment that is deemed standard of care.
- Subjects with PR/SD in whom CN/MET is not safe and feasible: in rare cases, subjects who were deemed eligible for CN/MET prior to study participation and have PR/SD to preoperative therapy may not be able to undergo CN/MET (for example, due to adverse events). These subjects will be required to provide a tumor biopsy, unless deemed unsafe or delays appropriate standard of care, in lieu of CN/MET. Subjects may continue study treatment with pembrolizumab 400 mg Q6W for up to 1 year (9 cycles), or until disease progression, death, unacceptable toxicity, or withdrawal of consent, whichever occurs first. The chance of experiencing severe toxicities related to study drug(s) that might preclude or delay surgery is less than 5%.

Following CN/MET, post-operative therapy for patients who achieved pre-operative CR/PR/SD will proceed as follows:

- Subjects with an R0 resection (NED, margins negative) or R1 resection (microscopic disease, margins positive) will continue receiving their assigned pembrolizumab-based combination therapy (with pembrolizumab dosing as 400 mg Q6W) for up to 9 cycles or until disease progression, death, unacceptable toxicity, or withdrawal of consent, whichever occurs first.
- Subjects with an R2 resection (macroscopic disease after surgery), or who had a pre-operative CR but did not undergo CN, will continue receiving their assigned pembrolizumab-based combination therapy (with pembrolizumab dosing as 400 mg Q6W) for up to 18 cycles or until disease progression, death, unacceptable toxicity, or withdrawal of consent, whichever occurs first.

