**Table 4 Adjuvant Treatment Regimen Per Cohort**

Cohort	Drug/Dose	Dose Frequency	Route of Administration	Schedule	Dose Levels
A/B/C	Pembrolizumab 400 mg	Q6W	IV	Day 1 of each 42-day cycle (Q6W)	N/A
B	Axitinib 5 mg titratable	BID	PO	Days 1-42 of each 42-day cycle	DL -2: 1 mg BID DL -1: 3 mg BID DL 1: 5 mg BID

Cohort	Drug/Dose	Dose Frequency	Route of Administration	Schedule	Dose Levels
					DL 2: 7 mg BID DL 3: 10 mg BID
C	TBD (agent to be determined)	TBD	TBD	TBD	TBD

Abbreviations: BID = twice daily; DL = dose level; IV = intravenous; N/A = not applicable; PO = by mouth; Q6W = every 6 weeks; TBD = to be determined.

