### 5.1.4 Continuation of Pembrolizumab-based Therapy Following CN/MET

Following CN/MET, post-operative therapy for patients who achieved pre-operative CR/PR/SD will proceed as follows (see Section 6.3):

- Subjects with an R0 resection (NED, margins negative) or R1 resection (microscopic disease, margins positive) will continue receiving pembrolizumab-based combination therapy (with pembrolizumab dosing as 400 mg Q6W) for up to 9 cycles or until disease progression, death, unacceptable toxicity, or withdrawal of consent, whichever occurs first.

- Subjects with an R2 resection (macroscopic disease after surgery), or who had a pre-operative CR but did not undergo CN, will continue receiving pembrolizumab-based combination therapy (with pembrolizumab dosing as 400 mg Q6W) for up to 18 cycles or until disease progression, death, unacceptable toxicity, or withdrawal of consent, whichever occurs first.
- Subjects will begin their first post-operative treatment no sooner than 21 days and no later than 42 days following CN and/or MET.

All subjects will be consented for optional tissue and blood collection at the time of disease progression.

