## 8.4 Analyses Plans

### 8.4.1 Analysis Population

- The analysis population for the primary outcome will be all subjects with pre- and post-pembrolizumab treatment tumor specimens that are evaluable for TICCs.
- The All Subjects as Treated (APaT) population will be used for the analysis of the secondary endpoints of clinical efficacy (ORR) and safety/toxicity outcomes. The APaT population consists of all subjects who received at least 1 dose of pembrolizumab-based therapy. At least 1 laboratory or vital sign measurement obtained subsequent to at least 1

dose of study treatment is required for inclusion in the analysis of each specific parameter. To assess change from baseline, a baseline measurement is also required.

- Subjects who undergo CN and/or MET will be evaluable for the exploratory clinical efficacy endpoints: pathologic response rate and R0 resection rate
- Additionally, subjects who receive continued pembrolizumab-based therapy will be evaluable for additional exploratory clinical endpoints (DFS/PFS at 1 and 2 years, median DFS and PFS)

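### Section 2.2.2 limits the DFS and PFS sets to subjects treated for 1 year, but Sections 8.1 and 8.4.1 do not; applied literally, 2.2.2 would select treatment completers

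*Combined protocol and SAP*

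**What the plan says.** Section 2.2.2 has two endpoint groups for continued therapy, each with a 1-year rate, a 2-year rate and a median. DFS is assessed "In subjects who obtain CR or PR/SD with R0 resection and are treated 1 year of pembrolizumab-based therapy". PFS is assessed "In subjects who obtain PR/SD and have residual disease following CN/MET and are treated with 1 year of pembrolizumab-based therapy".

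The treatment has a maximum length, not a fixed one. Under Section 5.1.4, R0 and R1 subjects are treated "for up to 9 cycles or until disease progression, death, unacceptable toxicity, or withdrawal of consent, whichever occurs first"; Sections 3.1 and 6.1.2.6 agree. Section 2.1.2 describes this course as "for up to 1 year (9 cycles) following CN/MET". R2 subjects, and those with a preoperative CR and no nephrectomy, may receive up to 18 cycles (2 years) under the same stopping conditions.

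The statistical section differs from 2.2.2:

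- Section 8.1 restates the endpoints and defines the groups by response and resection status only. Its 1-year rate is the share still free of disease or progression when the treatment year ends.
- Section 8.4.1 says that "subjects who receive continued pembrolizumab-based therapy will be evaluable for additional exploratory clinical endpoints", and lists the DFS and PFS measures there. Sections 2.2.2 and 8.1 list them as secondary, and the exploratory list in 2.2.3 does not name them.
- Section 8.4.3 reports them descriptively, timed from CN/MET.

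**The concern.** If the 2.2.2 set means subjects who actually received a year of treatment, then a subject who relapses in that year is excluded by the relapse itself. Membership would depend on the outcome being measured. The 1-year rate would say almost nothing, and the 2-year rate would become a rate among those already event-free at about 1 year.

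These are the only endpoints listed for the secondary objective on continued therapy. The trial is open-label and the sections are not ranked, so two analysts could follow the document in good faith and report very different rates from the same data. That choice is hard to settle credibly once results are known.

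**Working it through.** The plan gives no expected DFS or PFS rate, event count or power, so there is no stated figure to reproduce. The check asks what the literal reading of 2.2.2 would do.

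**Timing.** Postoperative cycles last 42 days (Table 4). Treatment starts "no sooner than 21 days and no later than 42 days following CN and/or MET" (Section 5.1.4). With no delays, dose 9 falls between day 21 + 8 × 42 = 357 and day 42 + 8 × 42 = 378 after surgery. Nine cycles span 9 × 42 = 378 days (54 weeks). Completing the course therefore means being on treatment at about month 12.

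**Closed form.** Assume exponential event times from surgery, S(t) = s^(t/365) with s the true 1-year rate, and treatment that stops at the event. Among those who reach dose 9 on day d:

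- 1-year rate = S(365) / S(min(d, 365))
- 2-year rate = S(730) / S(d)

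For s = 0.70, the 1-year rate runs from 0.70^(8/365) = 0.992 to 1. The 2-year rate runs from 0.70^(373/365) = 0.695 to 0.70^(352/365) = 0.709.

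| True 1-year / 2-year | Completers, 1-year | Completers, 2-year |
|---|---|---|
| 50% / 25% | 98–100% | 49–51% |
| 70% / 49% | 99–100% | 69–71% |
| 85% / 72% | about 100% | about 85% |

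**Size of the 2-year inflation.** Conditioning on being event-free at exactly 12 months gives S(24)/S(12) = s instead of s², an excess of s − s². This is 25 points at s = 0.5, 24 at 0.6, 21 at 0.7, 16 at 0.8 and 9 at 0.9.

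**Allowing for treatment until PD is confirmed.** Sections 7.1 and 7.1.3 let treatment run past first progression, with repeat imaging at 4–8 weeks in clinically stable subjects. A simulation used a start 3–6 weeks after surgery, scans every 12 weeks with progression dated at the scan, 0–30% per year stopping for toxicity independently of progression, and either no delay or 4–8 weeks of treatment until confirmation for everyone. The two medians are illustrative. The 15.1 months is the median PFS that Section 1.2.2.1 gives for pembrolizumab plus axitinib in the phase III trial in advanced RCC; the 36 months is assumed.

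| Median | All starters, 1-year / 2-year | Completers, 1-year | Completers, 2-year |
|---|---|---|---|
| 15.1 months | 65% / 36% | 100%; 95–98% with delay | 53–60% |
| 36 months | 84% / 65% | 100%; 98–99% with delay | 77–81% |

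The all-starter rates are slightly above the plain exponential values (57.6% / 33.2% and 79.4% / 63.0%) because progression is dated at the next scan and only subjects event-free at the start are counted. Across scenarios, 43–69% of starters (median 15.1 months) or 58–85% (median 36 months) reach dose 9; the rest would leave the set.

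**The case against.** The strongest reply is that the statistical section already has a sound set. Section 8.1 imposes no duration, and its 1-year rate makes sense only if subjects who relapse during the year are in the denominator. Section 8.4.1 requires only that continued therapy be received, and Section 6.3.1 keeps early discontinuers in the trial. This stands. A reader might infer from 2.2.2 that the planned 1-year DFS rate is about 100% by construction; the documents taken together do not support that.

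A second reply is that being treated for 1 year may simply mean assigned to the 1-year course. That works for R0 subjects. It fails for the PFS bullet: R2 subjects have residual disease but are assigned up to 18 cycles, so this reading would drop them from PFS.

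Three limits on size also stand. Treatment until PD is confirmed lowers the 1-year figure to as little as 95%. In Cohort B a subject who stops one drug for toxicity may stay on the other (Section 5.1.2.2), so not every toxicity stop would be a removal. The closed-form figures fit the 9-cycle course without delays and do not describe R2 subjects.

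A reader might also infer that R1 subjects have no endpoint, or belong with R0 because they share the 9-cycle course. Neither follows: R1 is defined as microscopic disease with positive margins, which fits residual disease. What is missing is a sentence saying so.

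**Conclusion.** The finding is a conflict between stated analysis sets, plus a conflict over whether DFS/PFS are secondary or exploratory. One of the sets, read literally, would bias the estimates badly: a 1-year rate of about 95–100% whatever the drug does, and a 2-year rate about 9 to 25 points too high for true 1-year rates of 90% down to 50%. This rests on an assumed exponential model and on a reading that 8.1 and 8.4.1 do not adopt, so it measures what the wording could cost, not what the trial is set to report. DFS and PFS are descriptive. The primary endpoint and the interim rules are untouched. The correction is worth making because it is nearly free and removes a choice that should not be left until results are known.

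**What to change.** - In both 2.2.2 bullets, replace the condition of being treated for 1 year with *start continued*, so that the set matches 8.4.1.
- State that stopping treatment early, for any reason, does not remove a subject from the DFS or PFS set.
- In 8.4.1, label DFS/PFS secondary, as in 2.2.2 and 8.1.
- State that R1 subjects count under residual disease, or report them on their own line. Do not move them into the DFS group.
- Reconcile the 1-year treatment period that 2.2.2 and 8.1 give for residual-disease subjects with the course of up to 18 cycles for R2 in 2.1.2, 3.1 and 5.1.4.

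The cost is wording only, with no extra patients. Section 7.1.2 continues imaging until progression, new anticancer treatment, withdrawal, death or end of study. Section 6.3.1 keeps early discontinuers in the trial, whereas 3.1 ends participation at unacceptable toxicity and 3.5 and 6.1.3.3 describe the follow-up year for completers. Those passages should be aligned, but in either case the subject stays in the set and is censored at the last assessment if no event is seen. The downside is that reported rates will be lower than a completers-only analysis would show.
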